#### **Introduction**

Heterotopic ossification (HO) is a common complication after surgical fixation of acetabular fractures, with incidence reported as high as 90%. HO can be a debilitating complication and surgical excision for more severe cases carries a high complication rate. Numerous strategies have been employed to prevent HO formation, but results are often conflicting, and the optimal treatment strategy remains controversial.

The most common interventions used to prevent HO formation are oral administration of indomethacin or single-dose external beam irradiation therapy (XRT). Despite the common use of indomethacin and observational data to support its use, more recent randomized controlled trials (RCTs) have failed to demonstrate any significant reduction in the incidence of severe HO when patients were administered 6 weeks of indomethacin versus placebo. In contrast, XRT has been shown to be effective against HO formation but there remain concerns surrounding the cost and potential long-term effects of XRT. Other authors have described debridement of the gluteus minimus muscle as a primary form of prevention, but the severe HO rate in the largest series of this approach (12%) is higher than that of numerous series that administered XRT as prophylaxis (1-5%).

Given the high incidence of HO, the impact of severe HO on outcomes, and the controversy regarding prophylaxis methods, there remains a need for randomized controlled trials (RCT) to determine optimal strategies for HO prophylaxis. The primary aim of this study is to assess the effect of XRT in preventing severe HO after acetabular surgery.

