Trial Interventions: Both arms will receive gluteus minimus debridement in the OR, which is considered the standard of care. If randomized to the treatment group, patients that undergo surgical fixation of an acetabular fracture via a posterior or combined anterior and posterior approach will undergo a single fraction of external beam radiotherapy to the surgical site within 72 hours of surgery. This treatment is currently the standard procedure performed for all patients who undergo a posterior or combined approach. The control treatment arm will only include gluteus minimus debridement in the OR and will not receive XRT.

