#### Data Collection

After obtaining informed consent, research personnel will record the baseline data on the study CRFs. They will obtain this information directly from the participant or proxy, from the participant's medical chart, and the participant's treating surgeon. Data collected will include patient demographics and injury characteristics, operative details, imaging, medical history, and complications (i.e. reoperation). 3 month post operative x-rays will be reviewed to assess HO formation. Additionally, any serious adverse events will be recorded. All data will be de-identified and recorded in REDCap.

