# Sample Size

We will enroll 100 patients across all sites. Enrolling 100 patients will give the study 80% power to detect an 88% reduction in the odds of severe HO using a two-sided alpha level of 0.05. The calculation assumes the rate of severe HO in the control group would be 20%.

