# **Statistical Analysis**

The primary analysis will follow the intention to treat principle, evaluating patients according to the group to which they were randomly assigned. To guard against any imbalances in randomization, the effect of XRT on our study outcomes using logistic regression models will be assessed, which will include a treatment indicator and adjusted for head injury, mechanical ventilation, acetabular hip dislocation, and associated fracture pattern. An as-treated sensitivity analysis will also be performed, in which patients will be evaluated according to the HO prophylaxis they received regardless of the treatment assignment. All analyses will be completed using R Version 4.2.2 (R Foundation for Statistical Computing, Vienna, Austria).

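### The as-treated sensitivity analysis compares non-randomized groups and can be biased in either direction; a prespecified complier-average estimate should stand beside the intention-to-treat result, with as-treated kept as exploratory.

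*Combined protocol and SAP*

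**What the plan says.** In the Statistical Analysis section, the primary analysis follows ITT, using logistic regression adjusted for head injury, mechanical ventilation, hip dislocation and associated fracture pattern. An as-treated sensitivity analysis follows, in which "patients will be evaluated according to the HO prophylaxis they received regardless of the treatment assignment". The section does not define receipt, does not say whether the four covariates apply to this second analysis, and gives no rule for reading a disagreement with ITT.

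Two statements under Trial Interventions bear on who might cross over. Patients assigned to XRT "will undergo a single fraction of external beam radiotherapy to the surgical site within 72 hours of surgery". Of XRT the protocol also says: "This treatment is currently the standard procedure performed for all patients who undergo a posterior or combined approach". No expected rate of non-delivery or crossover is given.

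On the data, the Data Collection section says "Data collected will include patient demographics and injury characteristics, operative details, imaging, medical history, and complications (i.e. reoperation". XRT receipt, its timing and other HO prophylaxis are not named. The Introduction lists indomethacin beside XRT as a common preventive measure.

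**The concern.** Grouping by treatment received replaces the randomized comparison with an observational one. It is unbiased only if, given any covariates used, the patients who depart from assignment have the same HO risk as those who do not.

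There is a plausible route to selective departure in each arm. Patients with head injury or on a ventilator may find it harder to reach radiotherapy in time, and the plan's choice of adjustment variables suggests that it regards them as prognostic. In the control arm, a surgeon worried about a high-risk patient may fall back on what the protocol calls current standard procedure. Both routes are inferences; the documents report neither.

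At stake is how a secondary result is read. A sensitivity analysis is expected to show whether the main finding is robust, and this one could contradict or inflate a correct ITT result. Readers may also take it as the effect of actually receiving XRT.

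**Working it through.** **The plan's own figure.** The Sample Size section says "Enrolling 100 patients will give the study 80% power to detect an 88% reduction in the odds of severe HO". The test is two-sided at the 5% level, and severe HO in controls is taken as 20%. An odds ratio of 0.12 gives an XRT risk of 0.12 × 0.25 / (1 + 0.12 × 0.25) = 0.0291. With 50 per arm, the unpooled standard error is √(0.20 × 0.80/50 + 0.0291 × 0.9709/50) = 0.0614. Then z = 0.1709/0.0614 = 2.785, and power is Φ(2.785 − 1.960) = 79.5%. The stated 80% reproduces, and nothing in it depends on the as-treated analysis.

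**Inputs for the bias check.** From the documents: 100 patients, 1:1 allocation (taken as 50 per arm), control risk p = 20%. Assumed, because the documents give no figures: no true XRT effect, a fraction f = 10% or 20% of one arm crossing over, crossing patients with risk r = 30% to 40%, and no covariate adjustment.

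**Formulas.** Patients remaining in the arm that loses members have risk a = (p − f·r)/(1 − f). The other arm plus the crossing patients has risk b = (p + f·r)/(1 + f). If XRT patients miss treatment, the as-treated contrast is a (XRT) against b (no XRT). If controls receive XRT, it is b against a, so the risk difference changes sign and the odds ratio inverts.

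| f | r | a | b | XRT missed: RD, OR | Controls given XRT: RD, OR |
|---|---|---|---|---|---|
| 10% | 30% | 18.9% | 20.9% | −2.0 points, 0.88 | +2.0 points, 1.14 |
| 20% | 30% | 17.5% | 21.7% | −4.2 points, 0.77 | +4.2 points, 1.30 |
| 10% | 40% | 17.8% | 21.8% | −4.0 points, 0.77 | +4.0 points, 1.29 |
| 20% | 38% | 15.5% | 23.0% | −7.5 points, 0.61 | +7.5 points, 1.63 |
| 20% | 40% | 15.0% | 23.3% | −8.3 points, 0.58 | +8.3 points, 1.72 |

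For the last row: a = (0.20 − 0.08)/0.80 = 0.150, b = (0.20 + 0.08)/1.20 = 0.233, OR = (0.150/0.850)/(0.233/0.767) = 0.58, and 1/0.58 = 1.72.

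If 10% of each arm crosses over without regard to risk, both groups stay at 20% and the odds ratio is 1.00. If 10% of each arm crosses over and all of them are high-risk, the two biases cancel under the null.

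**Complier-average estimate.** This is the ITT risk difference divided by the between-arm difference in the proportion receiving XRT. Under the null the numerator is 0.20 − 0.20 = 0, so the estimate is 0 in every row.

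**Chance of a misleading result.** In 20,000 simulated trials per scenario (50 per arm, no XRT effect), each direction should be significant in about 2.5% of trials. When high-risk patients miss XRT, a false benefit appears in 4.5% (f = 10%, r = 30%), 6.9% (f = 20%, r = 30%) and 13.8% (f = 20%, r = 38%). When high-risk controls receive XRT (r = 30%), a false harm appears in 4.3% and 7.0% at f = 10% and 20%, and a false benefit in only 1.4% and 0.8%.

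**With a real effect.** Apply an odds ratio of 0.12 within each risk group, with half the patients at 30% risk, half at 10%, and 10% selective crossover. The true effect in compliers is −16.0 points. As-treated gives −18.0 points if XRT is missed and −15.6 points if controls receive it. The complier-average estimate gives −16.0 points in both.

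**Precision.** Dividing by 0.9 or 0.8 widens the interval by 1/0.9 = 1.11 or 1/0.8 = 1.25. In simulation the standard deviation rose from 8.0 points to about 9.0 and 10.1, that is by about 12% and 26%.

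**The case against.** The plan already has the right order: ITT is primary, as-treated is only a sensitivity analysis, and no stated figure rests on it. That stands and limits the consequence.

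The crossover rates and risks above are assumed, and the table ignores adjustment, although head injury and ventilation are covariates in the plan's models. That also stands. Adjustment would remove part of the bias but not what comes from unmeasured severity. Its capacity is modest: about 20 events are expected under the null (20% of 100), and about 11.5 under the planned effect (10 + 1.5).

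A reader might infer that the trial will not collect XRT receipt at all. The documents do not support this. The data list is worded inclusively, the chart and treating surgeon are given as sources (in the sentence on baseline data), and the case report forms are not in the documents. A commitment to analyse by prophylaxis received also implies recording it. What can be said is that the item is not named, and that XRT, given after surgery, is not clearly an operative detail.

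The complier-average estimate has limits too. It applies only to patients who would follow either assignment, so it does not answer the as-treated question. It assumes monotonicity (nobody would receive XRT only if assigned to control) and the exclusion restriction (assignment affects HO only through XRT). No blinding is stated, so other prophylaxis given preferentially to controls could break the second assumption. Being a rescaled ITT effect, it gives essentially the same test of the null. All of this stands, and it is why the estimate should be added with its assumptions and not presented as a cure.

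**Conclusion.** The concern holds in a limited form. The as-treated comparison is non-randomized, and selective crossover of 10-20% can move its odds ratio, with no true effect, to 0.77-1.30 (crossing patients at 30% risk) or 0.58-1.72 (at 40%), before adjustment. The complier-average risk difference stays at about 0 in the same cases.

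It is tempting to conclude that the analysis will exaggerate the benefit of XRT. The documents do not support a direction. The description of XRT as standard procedure makes crossover by controls at least as plausible as missed treatment, and that would push towards harm if the crossing controls are high-risk. Nor is there a case for removing the as-treated analysis outright, since the two analyses address different questions. The primary ITT analysis and the power statement are unaffected.

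**What to change.** 1. Keep ITT primary and also report its unadjusted risk difference, so that the numerator of the ratio is visible beside the adjusted odds ratio.
2. Prespecify a complier-average estimate as the estimate of the effect of receiving XRT: the ITT risk difference divided by the between-arm difference in the proportion receiving XRT, with a bootstrap or delta-method confidence interval. State that it applies to compliers and assumes monotonicity and the exclusion restriction.
3. Keep the as-treated analysis only as non-randomized and exploratory, using the four covariates of the primary model. Define receipt, including how XRT delivered outside the 72-hour window is classified.
4. Name in the Data Collection section, for both arms: XRT received (yes/no), hours from surgery, reason for any departure from assignment, and any other HO prophylaxis given. Both analyses need the XRT items, and the record of other prophylaxis helps judge the exclusion restriction.

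The cost is some analysis-plan wording, one ratio and a few REDCap fields. The statistical price is a complier-average interval about 11-26% wider than the ITT interval at 10-20% crossover, and an estimate that does not independently test the robustness of a null result.

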# Data Management

All eCRFs will be completed by designated, trained site personnel. Research personnel will enter data as detailed on the CRFs into the secure University of Maryland, Baltimore REDCap system. Clinical site personnel will have a unique login and password for the system and will be able to view and modify data for participants recruited at their local site. The University of Maryland, Baltimore staff will monitor and oversee all data as it is collected across both sites, ensuring there is no missing, implausible, or inconsistent data. The trial will be conducted following GCP guidelines.

# **Ethics**

The University of Maryland, Baltimore, and Emory University will obtain ethics/IRB approval prior to commencement of participant enrollment.

Confidentiality

Information about trial participants will be kept confidential and will be managed in accordance with the below rules:

1) All trial-related information will be stored securely.

2) All trial participant information will be stored in locked file cabinets and accessible only

to site research personnel.

- 3) All paper and electronic CRFs will be identified only by a coded participant number.
- 4) All databases will be password protected.

If a participant revokes authorization to collect or use personal health information, the clinical site retains the ability to use all information collected prior to the revocation of participant authorization.

# Protocol Amendments

Any amendments to the study protocol which may affect the conduct of the study, the potential safety of, or benefits to participants (e.g., changes to the objectives, design, sample size, or procedures) will require a formal amendment to the protocol. Any protocol amendments will be approved by the Principal Investigator and may require approval by all applicable ethics committees and regulatory agencies. Clinical sites will also be required to submit amendment requests to their ethics committee to obtain approval for the amendment. Administrative changes (e.g., minor corrections or clarifications that have no effect on the way the trial is conducted) will not need to undergo a formal amendment process.

# Safety Reporting and Monitoring

Safety Plan HO Prophylaxis - Protocol v1 (2021.01.22) The safety plan for participants in this study is based on clinical experience with the trial interventions in completed and ongoing studies. The trial period during which AEs must be reported begins after the patient has consented and enrolled in the study and continues until the end of the participant follow-up period at their first post-operative visit. AEs recorded during this period will be followed through to resolution, or until the event is deemed chronic or stable.

The anticipated important safety risks are outlined below. Several measures will be taken to ensure the safety of participants, including the use of inclusion and exclusion criteria and close monitoring of participants. Administration of the study procedures will be performed in a setting in which participants are closely monitored for potential adverse events, and there is immediate access to trained personnel and adequate equipment and medicine to manage potentially serious reactions.

#### Definitions

#### Adverse Event (AE)

An AE is any untoward medical occurrence in a participant administered medicinal product and which does not necessarily have a causal relationship with this treatment. It can therefore include any unfavorable and unintended sign, symptom, or disease temporally associated with the use of an investigational medicinal product or other protocol-imposed intervention.

# Serious Adverse Event (SAE)

An AE should be classified as a SAE if any of the following criteria are met:

- It results in death (e.g., the AE causes or leads to death).
- It is life-threatening (e.g., the AE, in the view of the investigator, places the participant at immediate risk of death. It does not include an AE that, had it occurred in a more severe form, might have caused death.).
- It requires or prolongs inpatient hospitalization.
- It results in persistent or significant disability/incapacity (e.g., the AE results in substantial disruption of the participant's ability to conduct normal life functions).
- It results in a congenital anomaly/birth defect in a neonate/infant born to a mother exposed to the investigational medical product.
- It is considered a significant medical event by the investigator based on medical judgment (e.g., may jeopardize the participant or may require medical/surgical intervention to prevent one of the outcomes listed above).

# Unexpected Serious Adverse Event

Any SAE that meets all the following criteria:

• Is unexpected, in terms of nature, severity, or frequency, given the research procedures that are described in the protocol and informed consent document and the characteristics of the patients eligible for the trial.

• Is related or possibly related to treatment/procedures under trial; possibly related means there is a reasonable possibility that the incident, experience, or outcome may have been caused by the trial procedures or treatments.

• Suggests that participation in the trial may place participants or others at a greater risk of harm (including physical, psychological, economic, or social harm) than was previously known or recognized.

Some unanticipated problems may not classify as adverse events. To be considered an adverse event, the unanticipated problem must be an untoward or unfavorable medical occurrence in a trial participant.

Reporting AEs and Unanticipated Events Local Investigator Reporting The local investigator is responsible for ensuring that all AEs including SAEs that are observed or collected during the study are reported to the appropriate local IRBs and the Methods Center, in accordance with applicable regulatory requirements.

#### Event Reporting Timelines

Local site investigators will report SAEs within the following timelines:

• All deaths and immediately life-threatening events, whether related or unrelated, will be recorded and reported to the sponsor within 24 hours of awareness.

• SAEs, other than deaths and immediately life-threatening events, will be reported within 72 hours of site awareness.

SAE information must be submitted no later than 30 calendar days from the time the local investigator becomes aware of the event.

Clinical sites will follow local procedures for submitting safety reports and follow-up information to their local ethics committee.
